4.0 Selection and Withdrawal of Subjects

4.1 Inclusion Criteria

- Subjects must sign the consent to screen and take part in the study.
- Subjects must be at least 15 years of age.

4.2 Exclusion Criteria

- > Patients will only be enrolled once
- > Patients who do not meet the inclusion criteria
- > Patients with a current HCV diagnosis
- > Patients who underwent a liver transplant

4.3 Withdrawal of Patients

> Patients who do not wish to participate in the study can withdraw at any time.

5.0 Data Management and Analysis

- 5.1 Data Entry and Management
 - >Data will be entered into the electronic data capture system utilized by the Liver Institute PLLC.
 - >Data and results will be entered within a week after they are collected during the mid-study and end-of-study data collection phases.
 - >Data will be de-identified prior to analysis
- 5.2 Data Analysis
 - > A statistician will overlook and conduct final data analysis
 - > Data will be analyzed for trends at the end of the study
 - > Analysis will be completed using IBM SPSS statistics version 24
- 5.3 Results
 - Assuming similar response as obtained for breast cancer or cervical cancer projects, we expect 4% of the targeted population to respond.
 - Based on the prior data, we computed the trend of increase in number of new HCV patients added per year to the pool of diagnosed cohort.
 - According to mapping hep C¹¹, the total number of Antibody screening tests performed in 2016 is 53,580, or 4,465 per month, which is expected to be like current rates of 2019.
 - > We estimate that similar number of subjects will come for self-screening
 - We expected to, at minimum, double the number of screenings to 8,930 tests per month, which will be evaluated after each intervention period as defined in Figure 3. This increase will correlate with the increase in diagnosis rates per 100,000 from 776 to at least 1,552. These numbers will be used as measures of success for the project.
 - Assuming the current rate of 5.2% positive HCV tests holds, we expect at least 464 people to be HCV+ per month from the 8,930 people screened.
 - ➢ From the total number of HCV positive individuals, only 26.1% in Arizona get treatment, which correlates with 120 people per month from the screened population or total of 1440 by the end of the study. Considering there are multiple challenges to treatment and complete eradication, the goal of the study is to promote treatment for those with access to healthcare; expecting to increase treatment rate to about 30%.
 - Statistical data and trends of HCV prevalence over previous years, obtained from the Arizona Department of Public Health, will be compared with the study outcomes to assess the success rate of the study. we expect the number of screened individuals to double and the diagnosis rate to remain at 5.2%. A measure of success is therefore defined as 8,930 or more screening tests performed per month.

The proposed intervention aims to increase the rate of diagnosed individuals to identify more of the HCV infected population as predicted by Yahia BR, et al (Figure 7)¹⁸. By increasing the number of screened individuals, we predict a 4.0% increase in addition to the current 50% diagnosed and aware.

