1.3 Current Standards: Outreach, Screening, and Therapies

- Currently, there is no standard model of public hepatitis C education and screening promotion. Although approaches like newspaper or media advertisement were used in the past, their benefit remains unknown. On the contrary, there are published reports evaluating the benefit of media campaigns on awareness of breast and cervical cancer screenings. Evaluating the benefit of this project is quite challenging, a meta-analysis revealed short term response of 4% to mass education on improving awareness for mammogram and pelvic examination for breast and cervical cancers, respectively¹⁴. There are no prior studies to estimate the response to HCV screening education in the mass population.
- Current standards encourage HCV screening for individuals considered to be at risk. This includes baby boomers, individuals exposed to infected blood or illicit

drug users. However, these standards do not take into consideration the transmission of disease and other possible causes, leaving millions undiagnosed.

- There are a variety of tests that can detect the presence of Hepatitis C Virus, one of which utilizes anti-HCV ELISA test and is confirmed by HCV PCR. Additional methods include imaging studies and liver biopsies.
- Current standards of treatment include several antiviral medicines that effectively cure the disease in most cases. The course of treatment typically takes 12-24 weeks based on the genotype of disease, extent of liver damage and whether the patient was treated for hepatitis C in the past. In addition to antiviral therapy, complications like cirrhosis and subsequent complications can also be treated using different medical procedures or medicines to prevent risk of liver failure, portal hypertension and liver cancer¹³.
- The Arizona Department of Public Health lags three year on their data compilation and reporting. Most recent data available for review is from 2016.

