3.0 Investigational Plan

3.1 Study Design

- This is a prospective study performed over a 45-month period. The principal design plan will follow Figure 3 below.
- The study design is based on HCV prevalence order, which was determined based on statistical data from the Arizona Department of Health Services and rate of Hepatitis C per 100,000 (Figure 4). High prevalence counties (123+ cases per 100,000) including La Paz, Mohave, and Yavapai with a total targeted population of 391,999 individuals. Medium-prevalence Counties (101-123 cases per 100,000) are Coconino, Gila, Greenlee, Maricopa, Pima and Pinal with total targeted population of 4,724,421. Low-prevalence counties (<101 per 100,000) including Apache, Cochise, Graham, Navajo, Santa Cruz, and Yuma with a population of 490,388.

- For the initial 9 months the study will utilize direct communication methods (email and text messages) to reach high prevalence areas (Month 1-6), medium prevalence areas (Months 7- 12), and low prevalence areas (Month 13-18).
- The second phase of the study will utilize indirect communication methods (Newspapers and Radio advertisements) and similarly target areas of high prevalence (Month 12-24), medium prevalence (Month 25-30) and low prevalence (Month 31-36).
- The third and last phase is detected for shelter visits and homeless education in high prevalence areas (Month 37-39), mid-prevalence areas (Month 40-42) and low prevalence areas (Month 43- 45).
- This program will follow a streamline cascade of care with three complementary, consecutive portions: Patient education during intervention periods, connection to appropriate care and treatment during gap periods (Figure 3).
- The person responsible for conducting and implementing the project will be the program coordinator. The coordinator will be responsible for responding to calls or emails regarding the study in reference to the FAQ in Appendix 8.3. One hour daily, 5 days per week will be dedicated to answering emails and responding to voice messages or calls. The number of hours will be adjusted according to project performance and needs.

Phase 1: Direct Communication

1. Direct Customized Email Messages

Email messages are customizable and tailored to individual people. The expected response rate as compared to similar healthcare content is about 2%, 112,136 of our targeted group.

a. Generating Email List

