Email listings of Arizona residents will be obtained from National Data Group and mass emails will be sent through sendgrid.com.

b. Frequency and Resources

Emails will be sent out daily during intervention periods of 2 months followed by a 1month gap for two rounds for each of the different prevalence groups. A project coordinator at the Liver Institute PLLC will assure expectations and targeted numbers are met.

c. Email Content

The email content will follow the template in Appendix 8.1, including an introduction of the program coordinator, introduction to the project as well as brief background information on

the disease and its risk factors (Appendix 8.6). It will also include the steps that need to be taken and contact information to answer any questions.

d. Progress Monitoring

Updates will be obtained from the carrier company as documented proof of the number of emails sent. Information will also be collected on how many emails were rejected and how many were opened. This information will then be used to guide adjustments of upcoming steps if expected response rates are not reached.

2. Direct Text Messages

Response rates to text messages are similar to that of emails at about 2% or 112,136 of the targeted population.

a. Generating Phone List

A list of Arizona residents phone numbers will be generated by National Data Group and messages will be sent to the targeted population through Verizon wireless.

b. Frequency and Resources

Text messaging will similarly follow the protocol described in Figure 3. Messages will be sent daily during the intervention period for 2-month followed by a 1-month gap for two rounds for each of the different prevalence groups.

c. Text Content

The text content will follow the template in Appendix 8.2. The message will be brief in comparison to the email content. It will include an introduction of the program coordinator, introduction to the project, the steps that need to be taken to get screened and a link to more information and background on the disease. It will additionally include contact information to answer any questions or connect to screening and treatment resources.

d. Progress Monitoring

Updates will be obtained from the carrier companies as to how many messages were sent daily and how many were rejected. This information will then be used to guide further changes or alterations if expected response rates are not reached.

Phase 2: Indirect Communication

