1. Newspapers, Advertisement Content, and Duration

Newspaper advertisements are assumed to generate a response rate of 2% or 112,136 of the targeted population. However, according to the local newspaper statistics, the response rate is expected to be higher.

a. Newspapers

The most common local newspaper in Arizona is The Arizona Republic. Both newspapers are well-rounded, published daily or weekly and readily available to the public. This newspaper serves all counties in Arizona, making it efficient and more accessible to all members of the population.

The Arizona Republic – Best Life

According to republic media.com, "Best Life" is the section inside the Arizona Republic dedicated for active, healthy adults and include preventative health tips and postings. This section is published weekly on Mondays and typically generates 46% response rate from the reader population.

The Arizona Republic – Overview

Since the previous section focuses on health-conscious individuals, another post will be published in the overview section, which is distributed daily. According to republicmedia.com, this section reaches 1.1. million adults weekly in the Phoenix area, 32% of local residents. Advertising through the Arizona Republic is therefore likely to generate the expected response rate and reach the majority of our targeted population.

- b. Duration and Monitoring
 - The hepatitis C newspaper advertisement will run similarly to other communication methods during the intervention periods; in 2-month intervals followed by 1-month gap for two rounds for each of the different prevalence groups.
 - Data collection and monitoring will be based on screening numbers during the gap periods. The project coordinator will be responsible for communicating with the magazine to make adjustments as needed.
- c. Advertisement Content
 - The content of the newspaper advertisement will be an infographic designed to present background information on the disease, a brief explanation of the program and its rationale and next steps that need to be taken.
 - The infographic will be designed by the program coordinator to display the information in a simple and clear format to comply with the newspaper's requirements.

2. Social Media

The third approach aimed to target the remaining 33%; 835,414 is social media: including radio and YouTube advertisements. This method is expected to generate a response rate of about 2%.

a. YouTube ➤ Type of Advertisement

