3.2 Subjects

The targeted study population consists of the entire Arizona population 15+ years of age. According to the ADHS 2017 vital statistics, this age range makes up 80% of the population and a total of 5,606,808 people. The targeted population is divided and ordered as below based on two parameters: known hepatitis C prevalence rates and risk, and the optimal method of communication.

1. Adults (45+)

Baby boomers are 5 times more likely to have hepatitis C than adults from any other age group⁴. According to AZ DHS population statistics, this group makes up 51% of the targeted population; 2,864,689 people. We hypothesize that older people are not exposed to social media as adolescents and young adults are. Therefore, it is important to utilize Email, direct text messages and newspaper outreach to reach this population.

2. Nasal and Injection Drug Users

Another extremely high-risk subgroup is nasal and injection drug users. Figure 5 below shows the rate of HCV positive antibody tests compared to the percentage tested categorized by risk factors. The results indicate 88% of the HCV positive clients had history of nasal drug use compared to 69% amongst all clients¹. We believe reaching out to this community would be an essential step in diminishing hepatitis C. To reach out to this group we plan on distributing pamphlets to treatment and rehabilitation entities.

3. Homeless

Another high-risk subgroup likely to develop infectious diseases is the homeless. According to Phoenix Rescue Mission, there are over 36,000 homeless people in Arizona, 71% of which are in Maricopa county⁸. In addition to their lack of awareness, this group likely do not have access to healthcare or healthy living environments, making them even more prone to fatal viruses and diseases. The most appropriate method to reach this subgroup would be through homeless shelter visits.

4. Adults (20-44)

This age groups makes up about 40% of the targeted population; 2,273,230 people. This group is likely exposed to social media as well as newspapers and direct communication methods such as email and text messages.

5. Millennials / Adolescents (<19 years of age)

We believe this age group, consisting of 8% of the targeted population; 468,889 people, would be equally responsive to social media and directed Emails and text messages. With the growing impact social media has on this category, it has more potential of engaging them than any other means of communication would.

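### The 2% per-channel response, the 4% overall response and the fixed mark of 8,930 tests a month are not derived from one another, so the success mark follows block size rather than outreach performance

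*Protocol*

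**What the plan says.** **Target.** Section 3.2 defines the target as everyone aged 15 or over: "this age range makes up 80% of the population and a total of 5,606,808 people". Section 3.1 splits it into three prevalence blocks. The high block is "La Paz, Mohave, and Yavapai with a total targeted population of 391,999 individuals"; the medium block has 4,724,421 people and the low block 490,388.

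**Per-channel response (3.1).**
- Email: "The expected response rate as compared to similar healthcare content is about 2%, 112,136 of our targeted group".
- Text: "Response rates to text messages are similar to that of emails at about 2% or 112,136 of the targeted population".
- Newspapers: "Newspaper advertisements are assumed to generate a response rate of 2% or 112,136 of the targeted population", with a remark that the true rate should be higher.
- Social media and radio: about 2%, aimed at a remainder of 835,414 people.

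For email and text, 3.1 says that later steps will be adjusted if the expected response is not reached.

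**Overall response (5.3).** By analogy with breast and cervical cancer campaigns, "we expect 4% of the targeted population to respond". Section 1.3 describes the source figure as a "short term response of 4% to mass education on improving awareness".

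**Success mark (5.3).** Baseline testing is 53,580 a year, or 4,465 a month, and "We estimate that similar number of subjects will come for self-screening". The mark is at least a doubling, to 8,930 tests a month, checked at the close of each intervention period.

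**Timing (3.1).** Phase 1 gives each block six months (1-6, 7-12, 13-18), which matches two rounds of two active months and one gap month. The same sentence also describes Phase 1 as the first nine months.

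**The concern.** Three planning figures do work in this protocol. The channel response triggers mid-study changes, the overall response states what the programme should yield, and the doubling decides success. They should come from one assumption, but nothing links them. The protocol does not say whether channel responses add or overlap, over what period the 4% accrues, or whether a response is an opened message or a completed test.

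The success mark is also one fixed number, applied in turn to blocks whose target populations differ twelve-fold. If the mark does not scale with the block, outreach that performs exactly as planned can miss it in a small block, and outreach far below plan can meet it in a large one. The result would then say little about how well a communication method worked, which is the comparison the study is meant to make.

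**Working it through.** **Reproducing the plan's figures**
- 391,999 + 4,724,421 + 490,388 = 5,606,808, as in 3.2.
- 0.02 × 5,606,808 = 112,136, as in 3.1.
- 53,580 / 12 = 4,465, and 2 × 4,465 = 8,930, as in 5.3.

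**Whole-study volumes**
- Overall 4%: 0.04 × 5,606,808 = 224,272; over 45 months, 4,984 a month.
- Doubling: 4,465 × 45 = 200,925, or 3.6% of the target. This is 90% of the 4% figure (200,925 / 224,272 = 0.896).
- Email plus text: 2 × 112,136 = 224,272, the same as the whole 4%.
- All channels, if they add: 3 × 112,136.16 + 0.02 × 835,414 = 353,117 (6.3%). If the social-media 2% applies to the full target, 4 × 112,136.16 = 448,545 (8.0%).

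**Phase 1 by block**

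Assumptions: one response is one completed test; email and text add, so 4% of each block responds; background testing stays at 4,465 a month and counts towards the 8,930 whichever block is active; each block lasts six months.

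Tests a month = 4,465 + 0.04 × N / 6.

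Share of expected response needed = (4,465 × 6) / (0.04 × N) = 26,790 / (0.04 × N).

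| Block | N | Expected responders | Added a month | Total a month | Share needed |
|---|---|---|---|---|---|
| High | 391,999 | 15,680 | 2,613 | 7,078 | 171% |
| Medium | 4,724,421 | 188,977 | 31,496 | 35,961 | 14.2% |
| Low | 490,388 | 19,616 | 3,269 | 7,734 | 137% |

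Put as a response rate, the high block needs 26,790 / 391,999 = 6.8% and the low block 26,790 / 490,388 = 5.5%, against 4% expected.

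**Sensitivity to the window and to overlap**
- *All tests fall in the four active months:* high 4,465 + 15,680 / 4 = 8,385 (misses); low 4,465 + 19,616 / 4 = 9,369 (passes); medium passes at 17,860 / 188,977 = 9.5% of expected response.
- *Phase 1 lasts nine months, split equally (my assumption):* high 4,465 + 15,680 / 3 = 9,692 and low 4,465 + 19,616 / 3 = 11,004, so both pass. The shares needed are 85% (high), 7.1% (medium) and 68% (low).
- *Email and text reach the same people (2% net, six months):* high 5,772 and low 6,100 miss; medium 20,213 passes at 28%.

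In every variant the share needed in the high block is 4,724,421 / 391,999 = 12 times that in the medium block.

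**The case against.** The best defence is that 8,930 is stated as a minimum, and a floor below an expectation is no contradiction. That stands for the study as a whole: the doubling is 90% of the 4% figure, so those two nearly agree. It does not help in a block where the plan's own expected volume lies below the supposed floor.

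Second, overlap between channels is to be expected. Section 3.3 has everyone targeted repeatedly and section 4.2 enrols each person once, so the channel figures may never have been meant to add. That is fair, and it means email plus text exhaust the 4% only if there is no overlap. But the overlap is not stated, and allowing for it lowers the block totals further.

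Third, the 2% may mean engagement with a message, since email monitoring counts rejected and opened messages. If so, the block totals above do not follow, and the protocol has no stated testing expectation per channel. The gap is then one of definition, and it still needs closing.

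A reader might infer two stronger claims. One is that a Phase 1 delivering about a third of its expected response succeeds under 5.3 and fails under 3.1. Pooled over 18 months, 80,370 / 224,272 = 35.8% would indeed suffice. But 5.3 does not pool: at that level the high and low blocks reach only about 5,400 and 5,640 tests a month and miss. Section 3.1 has an adjustment trigger and no failure rule. The share itself runs from 18% (nine months) to 72% (both channels reaching the same people). The other claim is that the 4% is not testing uptake. Section 1.3 is ambiguous on this, and the cited meta-analysis is titled as one of effects on behaviour change. Neither claim is supported.

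**Conclusion.** The point holds as a failure to reconcile figures that the protocol itself fixes. The per-channel 2% does not fit the overall 4% unless overlap is stated, and neither is linked to a success mark that ignores block size.

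With six-month blocks and full planned response, the mark is missed in the high block (7,078) and the low block (7,734), and met in the medium block at about 14% of plan. These figures rest on one response being one test, additive channels, a constant background of 4,465 and the month 1-18 timetable. Which blocks miss depends on the window: the low block passes if all tests fall in four active months, and both small blocks pass on the nine-month wording. The twelve-fold difference in the share of expected response required does not depend on the window.

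**What to change.** In sections 3.1 and 5.3:
1. Define a response as a completed screening test presented with a study code.
2. Adopt one response assumption, state how much the channels overlap given that each person enrols once, and restate the overall percentage to match.
3. Derive both the adjustment trigger and the success mark from that assumption, as added coded tests per block, scaled to the block's target population and its evaluation window. This replaces the single figure of 8,930.
4. Reconcile the nine-month description of Phase 1 with months 1-18, and state which months count in each evaluation.

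The cost is a few rewritten figures and sentences. Some expected counts will look less favourable. Because section 3.4 already makes codes specific to the outreach method, counting coded tests should need little new data collection.

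### Success is a fixed 8,930 tests a month, twice one 2016 count, and section 5.3 does not say which tests count, so the threshold does not measure the outreach effect

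*Protocol*

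**What the plan says.** All the figures are in Protocol section 5.3. The baseline is one year's antibody test count, "53,580, or 4,465 per month, which is expected to be like current rates of 2019". A similar number of subjects is expected to come forward for self-screening, so the plan is to "double the number of screenings to 8,930 tests per month, which will be evaluated after each intervention period". The rule is then stated outright: "A measure of success is therefore defined as 8,930 or more screening tests performed per month".

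The same 8,930 is also described in section 5.3 as people screened, and the doubling is restated for screened individuals. Section 4.2 allows each person into the study once ("Patients will only be enrolled once").

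Other parts of the protocol bear on what could be counted:

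- Section 3.4 provides time-limited promotion codes specific to each outreach method.
- The Synopsis has the laboratory send results to the study coordinator.
- Section 3.1 sets the duration at 45 months and brings in the high, medium and low prevalence tiers one after another.

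Patients screened is a primary endpoint (section 2.2).

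**The concern.** The threshold is a constant derived from a single year, and no passage rebases it during the study. If it is applied to all antibody tests, the comparison is an uncontrolled before-after one against an old level. Any rise in testing for other reasons then helps to meet it, and a declaration of success would not show that outreach raised screening.

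If it is applied only to code-redeemed tests, the count and the baseline are of different kinds: one comes from the study alone, the other from all sources. Because the rule concerns a primary endpoint, the study's main claim depends on which reading is used, and section 5.3 does not settle it.

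**Working it through.** **The plan's own figures.** 53,580 / 12 = 4,465 and 2 × 4,465 = 8,930. Both reproduce exactly, as does the expected number of positives: 5.2% × 8,930 = 464.

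**Which tests does 8,930 count?** Section 5.3 adds a similar number of self-screeners to the existing tests: 4,465 + 4,465 = 8,930. That points to a total from all sources. The section's 4% response expectation fits this reading: 4% × 5,606,808 = 224,272 persons, which spread evenly over 45 months (an assumption) is 4,984 a month. This is close to 4,465 and well short of 8,930. The text never states the reading, however, and the codes in section 3.4 would permit an outreach-only count.

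**All-tests reading.** Let g be the assumed annual growth in background testing (the protocol gives none) and t the years of growth. Background volume is B = 4,465 × (1 + g)^t, and the share of the required increase supplied without outreach is (B − 4,465) / 4,465. I centre the 2016 count on mid-2016 and assume a mid-2019 start.

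- Growth from 2016 to Month 45: t = 3 + 45/12 = 6.75 years.
- Growth only from 2019, accepting the protocol's statement that 2019 resembles 2016: t = 45/12 = 3.75 years.

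| g per year | B at Month 45, from 2016 | Share of 4,465 | B at Month 45, from 2019 | Share of 4,465 |
|---|---|---|---|---|
| 2% | 5,104 | 14% | 4,809 | 8% |
| 5% | 6,207 | 39% | 5,361 | 20% |
| 8% | 7,506 | 68% | 5,959 | 33% |

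The threshold is met with no outreach effect when (1 + g)^t = 2. That gives g = 2^(1/6.75) − 1 = 10.8% a year from 2016, or 2^(1/3.75) − 1 = 20.3% a year from 2019. Moving the start to 2.5 or 3.5 years after mid-2016 changes the first figure to 11.7% or 10.0%.

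Month 45 is the far end. At a first check two months into the study, with growth from 2016, t = 3 + 2/12 = 3.17 years and the shares are about 6%, 17% and 28%.

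**Code-only reading.** Background growth adds nothing. But if outreach brings in the similar number that section 5.3 expects, about 4,465 a month, the code-redeemed count reaches only 4,465 / 8,930 = 50% of the threshold. Outreach could perform exactly as predicted and fail.

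**The case against.** The strongest reply is that the study's own data are outreach-specific. Screening needs a promotion code and a signed consent, and results go to the coordinator. Impact in the newspaper and shelter phases is read from screening numbers in the gap periods. If only those screens count, routine growth is never credited and the table above does not apply. This stands as far as it goes: section 5.3 leaves the reading open, so one cannot say that growth *will* be credited. It does not rescue the threshold, which then compares unlike counts.

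A reader might infer several stronger points that the protocol does not support:

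- *That 2016 test volume is the only comparator.* Section 5.3 also names a diagnosis rate (776 to at least 1,552 per 100,000) and a comparison with state prevalence trends. The first is another fixed doubling and the second concerns prevalence, so neither adjusts for a trend in testing, but they are stated.
- *That the protocol concedes testing is rising.* The sentence "we computed the trend of increase in number of new HCV patients added per year" concerns diagnosed patients, not tests.
- *That reporting lag prevents correction.* The statement "The Arizona Department of Public Health lags three year on their data compilation and reporting" is about the state department. The 53,580 comes from a different cited source, for which no lag is given.
- *That the baseline is declared flat to Month 45.* Flatness is stated only to 2019; beyond that it is inferred from the unchanging threshold.
- *That counting tests causes the growth bias.* It does not. The unit fault is inconsistent wording. The protocol does not say whether the 2016 count includes repeat tests; if it does, doubling it in once-enrolled persons would be harder, not easier.

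Trend adjustment could be left to a statistical analysis plan. The success rule itself is fixed here, though, and that is the point at issue.

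**Conclusion.** The point holds in this form: the success threshold is a constant, twice one 2016 count, with no stated rebasing, no statement of which tests count and no consistent unit. On neither reading does reaching or missing 8,930 measure the effect of outreach.

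The size applies only to the all-tests reading and rests on assumed growth rates of 2% to 8% a year. Between 8% and 68% of the required increase by Month 45 could come from background growth, depending on the rate and on whether growth runs from 2019 or 2016. Reaching the threshold without any outreach effect would need about 20% or 10.8% a year respectively. Earlier checks are affected less. Confidence is medium, because both the growth rate and the intended count are unknown. The rule should be changed, since it governs a primary endpoint and the change is small.

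**What to change.** In section 5.3:

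1. Define the success measure as unique persons screened with the method-specific promotion codes already planned in section 3.4, reported by prevalence tier and month.
2. Judge the increase against routine (non-code) test volume at the partner laboratory in the same months. The code count alone is not enough, because some redeemers might have been tested anyway; a matching fall in non-code volume would show this.
3. Use one unit throughout, for the code and non-code counts alike.
4. Keep the 2016 figure as context and not as the threshold.
5. As supporting evidence in Phase 1 only, compare with tiers not yet contacted: the medium tier in Months 1-6 and the low tier in Months 1-12, using the month ranges in section 3.1. Allow for the tiers having been chosen to differ in prevalence and differing greatly in size (391,999, 4,724,421 and 490,388). This comparison is not available for later months or for Phases 2 and 3.

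The cost is a rewording and a request to the laboratory for monthly counts, by county for item 5. I assume these are available. The drawback is reliance on one laboratory's volume, which may not track testing in the whole state.
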